4.1 Prohibited Medications

All subjects must agree to discontinue all prohibited medications during the screening period in order to meet the protocol-specified washout periods. [Table 4.1-1](#) provides the required duration of washout for selected prohibited medications. All other prohibited medications must be discontinued at least 24 hours before the first dose of IMP in Phase A.

Table 4.1-1 List of Medications Prohibited Before the Trial		
	Medication	Required Duration of Washout
1.	Antipsychotics (depot or long-acting injectable)	One full cycle plus 1/2 cycle
2.	Monoamine oxidase inhibitors	14 days
3.	Antipsychotics (oral)	7 days
4.	Benzodiazepines	7 days
5..	Hypnotics, including non-benzodiazepine sleep aids	7 days

Protocol 331-201-00079

Table 4.1-2 lists all medications prohibited during the trial, including exceptions, where appropriate.

Table 4.1-2 List of Medications Prohibited During the Trial	
1.	All psychotropic agents including, but not limited to, the following: a) Antipsychotics, including depot or long-acting injectable formulations b) Anticonvulsants c) Antidepressants other than those prescribed as IMP d) Mood stabilizers (ie, lithium) e) Benzodiazepines, except when used to manage treatment-emergent AEs such as agitation and anxiety (See Table 4.1-3) f) Hypnotics, including ramelteon and other non-benzodiazepine sleep aids, except for specific medications when used to manage treatment-emergent AEs related to insomnia ^a g) Stimulants h) Opioid analgesics, unless permission is obtained from the medical monitor. Permission for opioid use may be considered for a documented and clinically appropriate indication (eg, episodic pain condition, tooth extraction) if prescribed at a medically appropriate dose and frequency. i) Nutritional supplements and non-prescription herbal preparations with central nervous system effects (eg, St. John's Wort, omega-3 fatty acids, kava extracts, gamma-aminobutyric acid supplements, etc)
2.	Investigational agents
3.	CYP2D6 inhibitors or CYP3A4 inhibitors and inducers. The medical monitor should be consulted for any questions regarding the potential for pharmacokinetic interactions with concomitant medications used by subjects during the trial. See Table 4.1-4 below provides a select list of CYP2D6 inhibitors and CYP3A4 inhibitors and inducers which are prohibited within 14 days prior to the first dose of brexpiprazole in Phase A or Phase B (as appropriate to the subject's point of entry into the trial) and for the duration of the trial.
4.	Barbiturates, except for the treatment of migraine headaches, provided that in the opinion of the investigator the dosing is medically appropriate.
5.	Varenicline

^aNon-benzodiazepine sleep aids (ie, zolpidem, zaleplon, zopiclone, and eszopiclone only) are permitted for the treatment of insomnia for up to 7 days total in Phase A, up to 7 days total in Phase B, and up to 7 days total in Phase C, but not on the same day as administration of a benzodiazepine, regardless of indication. For the non-benzodiazepine sleep aids, sites should only utilize 1 of the listed medications that are approved for this indication in their respective countries and the country-specific prescribing information is to be used to determine the maximum allowable daily dose for the treatment of insomnia. Non-benzodiazepine sleep aids must not be administered within 12 hours prior to scheduled efficacy and safety assessments, including EPS scales. Investigators are encouraged to delay scale administration until 12 hours have elapsed, if at all possible. However, if delaying administration of efficacy and safety scales is not feasible, the scales should still be administered and the use of the sleep aid documented, including a notation of the drug name, dose, and time of administration on the eSource.

Table 4.1-3 presents the protocol-specified oral benzodiazepines that can be used as rescue medication in this trial. Oral lorazepam and oral oxazepam are to be used, if available. In countries or at investigative sites where lorazepam and oxazepam are not

Protocol 331-201-00079

available, use of oral diazepam or oral clonazepam may be acceptable if prior authorization is obtained from the medical monitor.

Table 4.1-3 Oral Benzodiazepine Rescue Therapy During the Trial

Oral Benzodiazepine ^a	Maximum Allowable Weekly Dose (mg/week)		
	Phase A	Phase B	Phase C
Lorazepam ^b	12	10	6
Oxazepam ^b	180	150	90
Diazepam ^{b,c}	60	50	30
Clonazepam ^{b,c}	6	5	3

^aBenzodiazepines must not be administered within 12 hours prior to scheduled efficacy and safety assessments, including EPS scales. Investigators are encouraged to delay scale administration until 12 hours have elapsed, if at all possible. However, if delaying administration of efficacy and safety scales is not feasible, the scales should still be administered and the use of benzodiazepine documented, including a notation of the drug name, dose, and time of administration on the eSource.

^bThe following guide should be used to determine approximate lorazepam equivalents:

1 mg lorazepam = 15 mg oxazepam = 0.5 mg alprazolam = 5 mg diazepam = 0.5 mg clonazepam.
Short-acting benzodiazepines are to be used whenever possible. The prescribed benzodiazepine should be discontinued as soon as the AE for which it was initiated subsides, as per the investigator's discretion to avoid any withdrawal effects.

^cIn countries or institutions where no short-acting benzodiazepines are commercially available, use of oral diazepam or oral clonazepam may be acceptable if prior authorization is obtained from the medical monitor.

Table 4.1-4 below provides a select list of CYP2D6 inhibitors and CYP3A4 inhibitors and inducers which are prohibited within 14 days prior to the first dose of brexpiprazole in Phase A or Phase B and for the duration of the trial.

Protocol 331-201-00079

Table 4.1-4 List of Medications Prohibited During the Trial: CYP2D6 Inhibitors and CYP3A4 Inhibitors and Inducers		
Selected CYP2D6 inhibitors^a	Selected CYP3A4 inhibitors	Selected CYP3A4 inducers
celecoxib hydroxyzine chloroquine methadone chlorpheniramine moclobemide clemastine clomipramine pyrilamine diphenhydramine quinidine terbinafine halofantrine tripelennamine	amiodarone fluvoxamine amprenavir indinavir aprepitant itraconazole chloramphenicol ketoconazole cimetidine nefazodone clarithromycin nelfinavir clotrimazole (if used orally) quinupristin/dalfopristin delavirdine ritonavir diltiazem saquinavir erythromycin troleandomycin fluconazole verapamil	carbamazepine oxcarbazepine phenytoin dexamethasone primidone efavirenz rifampin nevirapine St. John's Wort phenobarbital troglitazone

^aFluoxetine, paroxetine, and duloxetine are protocol-defined ADTs that are also CYP2D6 inhibitors. In order to limit the potential higher exposure of brexpiprazole when coadministered with such inhibitors, the upper limit of the therapeutic ADT dose is limited to 40 mg for fluoxetine, 50 mg for paroxetine CR, and 60 mg for duloxetine.

4.2 Other Restrictions

The subject's best medical interests should guide the investigator in the management of conditions that are pre-existing or that develop during the trial (intercurrent illness or AEs). The investigator should examine the acceptability of all concomitant medications not explicitly prohibited. In order to ensure that appropriate concomitant therapy is administered, it is essential that subjects be instructed not to take any medications (either self-administered non-prescription drugs or prescription therapy prescribed by another physician) without prior consultation with the investigator. In particular, the investigator should caution the subject about concomitant use of the following during the trial:

- Non-steroidal anti-inflammatory drugs, aspirin, or other drugs that interfere with coagulation since the combined use of psychotropic drugs that interfere with serotonin reuptake and these agents has been associated with an increased risk of upper gastrointestinal bleeding.
- Triptans (eg, sumatriptan, naratriptan, almotriptan, frovatriptan, rizatriptan, eletriptan, and zolmitriptan), linezolid, and methylene blue since there have been rare postmarketing reports of serotonin syndrome or serotonin syndrome-like reactions

Protocol 331-201-00079

(eg, mental status changes, hyperreflexia, autonomic effects, lack of coordination, and diarrhea) following the concomitant use of SSRIs or serotonin-norepinephrine reuptake inhibitors and these drugs.

All trial personnel should be familiar with the content of the IB for brexpiprazole in order to manage the subject's condition adequately and select appropriate concomitant medications, if needed.

5 Reporting of Adverse Events

5.1 Definitions

An AE is defined as any untoward medical occurrence in a patient or clinical trial subject administered a medicinal product and which does not necessarily have a causal relationship with this treatment. Adverse events would not include information recorded as medical history at screening for preplanned procedures for which the underlying condition was known and no worsening occurred. An adverse reaction is any untoward and unintended response to an IMP related to any dose administered.

A suspected adverse reaction is any AE for which there is a reasonable possibility that the IMP caused the AE. For the purpose of IND safety reporting, "reasonable possibility" means there is evidence to suggest a causal relationship between the IMP and the AE. Suspected adverse reaction implies a lesser degree of certainty about causality.

An SAE includes any event that results in any of the following outcomes:

- Death
- Life-threatening; ie, the subject was, in the opinion of the investigator, at immediate risk of death from the event as it occurred. It does not include an event that, had it occurred in a more severe form, might have caused death.
- Persistent or significant incapacity/disability or substantial disruption of the ability to conduct normal life functions.
- Requires in-patient hospitalization or prolongs hospitalization.
 - Hospitalization itself should not be reported as an SAE; whenever possible the reason for the hospitalization should be reported.
 - Hospitalizations or prolonged hospitalizations for social admissions (ie, those required for reasons of convenience or other non-medical need) are not considered SAEs.
- Congenital anomaly/birth defect.
- Other medically significant events that, based upon appropriate medical judgment, may jeopardize the subject and may require medical or surgical intervention to prevent one of the outcomes listed above; eg, allergic bronchospasm requiring intensive treatment in an emergency room or home,

Protocol 331-201-00079

blood dyscrasias or convulsions that do not result in hospitalization, or the development of drug dependency or drug abuse.

Nonserious adverse events are all AEs that do not meet the criteria for a "serious" AE.

Immediately Reportable Event (IRE)

- Any SAE.
- Any AE related to occupational exposure.
- Potential serious hepatotoxicity case (see [Section 5.4](#)).
- Pregnancies are also defined as IREs. Although normal pregnancy is not an AE, it will mandate IMP discontinuation and must be reported on an IRE form to the sponsor. Pregnancy will only be documented on the AE eSource if there is an abnormality or complication.

Clinical Laboratory Test Value Changes: It is the investigator's responsibility to review the results of all laboratory tests as they become available. This review will be documented by the investigator's dated signature on the laboratory report. For each abnormal laboratory test result, the investigator needs to ascertain if this is an abnormal (ie, clinically significant) change from Phase A baseline for that individual subject. This determination, however, does not necessarily need to be made the first time an abnormal value is observed. The investigator may repeat the laboratory test or request additional tests to verify the results of the original laboratory tests. If this laboratory value is considered medically relevant by the investigator (subject is symptomatic, requiring corrective treatment or further evaluation), or if the laboratory value leads to discontinuation, and/or fulfills a seriousness criterion, this is considered an AE.

Severity: Adverse events will be graded on a 3-point scale and reported as indicated on the eSource. The intensity of an adverse experience is defined as follows:

1 = Mild: Discomfort noticed, but no disruption to daily activity.

2 = Moderate: Discomfort sufficient to reduce or affect normal daily activity.

3 = Severe: Inability to work or perform normal daily activity.

IMP Causality: Assessment of causal relationship of an AE to the use of the IMP is defined as follows:

Related: There is a reasonable possibility of a temporal and causal relationship between the IMP and the AE.

Not Related: There is no temporal or causal relationship between the IMP and the AE.

Protocol 331-201-00079

5.2 Eliciting and Reporting Adverse Events

The investigator will periodically assess subjects for the occurrence of AEs. To avoid bias in eliciting AEs, subjects should be asked the non-leading question: “How have you felt since your last visit?” All AEs (serious and nonserious) reported by the subject must be recorded on the source documents and on the eSource provided by the sponsor. Serious AE collection is to begin after a subject has signed the ICF.

Use medical terminology in AE reporting. Adverse events should be reported as a single unifying diagnosis whenever possible or, in the absence of a unifying diagnosis, as individual signs or symptoms. Exacerbation or disease progression should be reported as an AE only if there are unusual or severe clinical features that were not present, or experienced earlier, or not expected based on the course of the condition.

A reported AE that undergoes a change in severity, seriousness, or toxicity should be reported as a new AE on the source documents and on the eSource provided by the sponsor.

In addition, the sponsor must be notified immediately by telephone, fax, or e-mail of any IREs according to the procedure outlined below, in [Section 5.3](#). Special attention should be paid to recording hospitalization and concomitant medications.

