Stabilization Phase (Phase B): Subjects who meet response criteria at the end of the Acute Treatment Phase will continue to a 12-week Stabilization Phase (Phase B). The purpose of the Stabilization Phase is to ensure subjects are able to maintain stability of depression symptoms at the dose of brexpiprazole optimized during Phase A. To proceed to the Double-blind Randomized Withdrawal Phase (Phase C), subjects must meet the stability criteria as defined in the blinded addendum to the protocol. Subjects not meeting stability criteria will be discontinued from the trial.

Protocol 331-201-00079

Double-blind Randomized Withdrawal Phase (Phase C): Subjects eligible for the Double-blind Randomized Withdrawal Phase will be randomized 1:1 to double-blind treatment with brexpiprazole + ADT or placebo + ADT for up to 26 weeks. Transition from the Stabilization Phase to the Double-blind Randomized Withdrawal Phase should not be made evident to the subject. During the Double-blind Randomized Withdrawal Phase, subjects will be evaluated in the clinic at biweekly visits for the first 2 visits and monthly visits thereafter. Subjects meeting the criteria for relapse as defined in the blinded addendum to the protocol will be withdrawn due to lack of efficacy.

Follow-up: Subjects who are discontinued, withdrawn, or complete the trial will be followed up for safety 21 (+2) days after the last dose of investigational medicinal product (IMP) by telephone contact or clinic visit at the investigator's discretion. Subjects should be prescribed appropriate depression treatment as per the investigator or the subject's psychiatrist or primary care physician.

Protocol 331-201-00079

[figure not shown]

Figure 3.1-1 Trial Design Schematic

Protocol 331-201-00079

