7.6.1.3 Phase C

The incidence of the following events will be summarized by treatment group (brexpiprazole +ADT versus placebo + ADT):

- TEAEs
- TEAEs by severity
- Potentially drug-related TEAEs
- TEAEs with an outcome of death
- Serious TEAEs
- Discontinuations due to TEAEs

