5.6.1 Adverse Events

All adverse events (AE) will be coded by MedDRA System Organ Class (SOC) and Preferred Term (PT). A treatment-emergent AE (TEAE) is defined as an AE which starts after start of trial medication), or an AE continues from baseline of the specific phase and becomes serious, worsening, trial drug-related or results in death, discontinuation, interruption or reduction of trial medication during this phase. The incidences of the following treatment-emergent adverse events (TEAEs) will be summarized by treatment groups:

- TEAEs by severity
- Potentially drug related TEAEs
- TEAEs with an outcome of death
- Serious TEAEs
- Discontinuations due to TEAEs

Listing and incidences of AEs above will be tabulated by treatment for Phase B safety sample and Phase C safety sample, respectively. Deaths, SAEs, and AEs leading to discontinuation from trial will be listed by phase for the enrolled sample.

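### The rule for re-reporting adverse events is not limited to worsening, so a carried-over AE that becomes milder in Phase C can be counted as a new Phase C TEAE, against the intent of the SAP

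*Protocol*

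**What the plan says.** **Reporting rule.** Protocol 5.2 states: "A reported AE that undergoes a change in severity, seriousness, or toxicity should be reported as a new AE". It does not restrict the change to an increase.

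**Severity scale.** Protocol 5.1 states: "Adverse events will be graded on a 3-point scale and reported as indicated on the eSource". The grades are mild, moderate and severe.

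**TEAE definition.** SAP 5.6.1 has two parts. The first covers new events: "A treatment-emergent AE (TEAE) is defined as an AE which starts after start of trial medication". The second covers carried-over events, which qualify when "an AE continues from baseline of the specific phase and becomes serious, worsening, trial drug-related or results in death", or when the event leads to discontinuation, interruption or reduction of trial medication in that phase.

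**Displays.** For Phase C, Protocol 7.6.1.3 states: "The incidence of the following events will be summarized by treatment group (brexpiprazole +ADT versus placebo + ADT". The list includes all TEAEs, TEAEs by severity and potentially drug-related TEAEs. SAP 5.6.1 adds: "Listing and incidences of AEs above will be tabulated by treatment for Phase B safety sample and Phase C safety sample, respectively".

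**Design.** Protocol 3.1 has stabilized subjects, all on brexpiprazole + ADT, "randomized 1:1 to double-blind treatment with brexpiprazole + ADT or placebo + ADT for up to 26 weeks".

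**The concern.** The two documents treat an improving AE differently. The SAP's second part filters carried-over events so that improvement alone does not make one treatment-emergent. The Protocol's rule can turn the same improvement into a separate AE record. If that record is dated in Phase C, it satisfies the SAP's first part and the filter is never applied. Tying the first part to the first dose of the phase would not close the gap, because the new record would still start within the phase.

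The tables exposed are the comparative Phase C TEAE tables, which serve the secondary objective of safety and tolerability. Every subject reaches randomization on brexpiprazole and only the placebo arm stops it. Relief from a drug side effect could therefore be tabulated as a new event on placebo.

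**Working it through.** The plan states no figure on this point, so there is none to reproduce. The check is a reading of the text, followed by an illustration under assumed inputs.

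**Step 1: which events are affected.** On a three-grade scale, an AE can become milder and remain an AE only from severe to moderate or mild, or from moderate to mild. A mild AE that ends is a resolution, not a severity change. The issue is therefore confined to AEs that are moderate or severe and ongoing at randomization.

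**Step 2: follow one such event through the rules.** Take a moderate AE that began in Phase B and becomes mild in Phase C.

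- If it stays one record, it continues from the Phase C baseline. It has not worsened, become serious or met another listed ground, so it is not a Phase C TEAE.
- Under Protocol 5.2 it is re-reported as a new AE. If that record starts in Phase C and stands alone, the first part of the SAP definition makes it a Phase C TEAE.

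The same clinical course gives opposite classifications, depending only on how it was recorded.

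**Step 3: look for a rule that settles it.** Protocol 5.2 does not say what start date the new record takes, whether the parent record is closed, or how the two are linked. Protocol 5.7.1 asks only for current status. SAP 5.6.1 has no step to collapse split records before TEAEs are derived. The supportable conclusion is that the event *can* be counted, not that it always is.

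**Step 4: illustration of size.** Inputs:

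- n = 225 per arm, planned (Protocol 7.1).
- p = share entering Phase C with an ongoing moderate or severe AE. Not in the documents; assumed 5% to 15%.
- s = probability that such an AE becomes milder in Phase C, by arm. Not in the documents; assumed values are in the table.

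Formulas: added TEAE subjects per arm = n × p × s; placebo excess in percentage points = 100 × p × (s placebo − s brexpiprazole).

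| p | s placebo | s brexpiprazole | Added, placebo | Added, brexpiprazole | Placebo excess (points) |
|---|---|---|---|---|---|
| 0.10 | 0.2 | 0.2 | 4.5 | 4.5 | 0 |
| 0.05 | 0.5 | 0.3 | 5.6 | 3.4 | 1.0 |
| 0.10 | 0.4 | 0.2 | 9.0 | 4.5 | 2.0 |
| 0.15 | 0.7 | 0.2 | 23.6 | 6.8 | 7.5 |
| 0.05 | 0.2 | 0.4 | 2.3 | 4.5 | −1.0 |
| 0.15 | 0.2 | 0.4 | 6.8 | 13.5 | −3.0 |

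Rows 2 and 4 are the extremes when p is 5% to 15%, s is 50% to 70% on placebo and s is 20% to 30% on brexpiprazole: 100 × 0.05 × (0.5 − 0.3) = 1.0 and 100 × 0.15 × (0.7 − 0.2) = 7.5. The last two rows show that the sign reverses if improvement is more frequent on brexpiprazole.

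These are upper figures for the overall TEAE row, because a subject with another Phase C TEAE is already counted there. The effect shows more at preferred-term level.

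**The case against.** **The SAP's second part would be nearly empty.** If every severity change made an unlinked new record, worsening events would already qualify under the first part, and the words about continuing events would do little. On this view the SAP must mean the changed AE to be the same continuing event. That is a fair account of intent, but it shows the conflict without resolving it: the SAP contains no instruction that would let a programmer treat the two records as one.

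**The wording is softer than it may look.** Protocol 5.2 says *should*, not *must*, and assigns no start date. This stands, and it is why the conclusion is conditional.

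**Few subjects may qualify.** Subjects unable to tolerate the minimum dose are withdrawn, the dose must be stable for the last 4 weeks of Phase B, and exclusion criterion 39 removes subjects with clinically significant safety concerns before randomization. These rules may well keep p low. The documents give no value.

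**Other safety data are independent.** SAS, AIMS and BARS are compared by arm in their own right (Protocol 7.6.5, SAP 5.6.7.2), and laboratory, vital-sign and ECG analyses do not use AE records. TEAEs are also split by severity, so a stepped-down record appears at a lower grade. This limits the harm but does not remove the record from TEAE incidence or from potentially drug-related TEAEs.

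**Phase B.** A reader might extend the point to events that began in Phase A and eased in Phase B. The documents do not support that. SAP 5.1.2 and 5.6 use the Phase A baseline for Phase B safety, so such an event already arose after baseline and on trial medication, and no exclusion is bypassed. Phase B also has no comparator.

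**Conclusion.** The point holds in conditional form. Protocol 5.2 and SAP 5.6.1 conflict on an AE that continues into Phase C and becomes milder, and nothing in either document reconciles them. Such an AE can be counted as a new Phase C TEAE if its new record is dated in Phase C and is not linked to the parent.

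A reader might infer that the false TEAEs will fall mostly on placebo and will narrow or reverse the Phase C safety contrast. Withdrawal of brexpiprazole in that arm alone makes a placebo excess plausible, but no passage or figure establishes it. The range is 0 with equal improvement rates and about 1 to 7.5 points if improvement is more frequent on placebo, and it rests wholly on assumed inputs; the sign depends on them too. Even with no imbalance, both arms' TEAE incidence could include improvements that the continuing-event criteria leave out.

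The primary and secondary efficacy analyses, power, alpha and the EPS rating-scale analyses are not affected. The change should be made, but it concerns AE derivation only.

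**What to change.** **Protocol 5.2 and eSource guidance.** Limit the new-AE rule to an increase in severity or an event becoming serious. Record a decrease as an update to the same AE, keeping the onset date of that AE.

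**SAP 5.6.1.** State that consecutive records of the same AE are linked to the parent onset before TEAEs are derived. State also that a record created only because severity fell is not a Phase C TEAE unless it meets another continuing-AE criterion.

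**Data already collected.** The SAP linkage step is enough: a programming rule that joins consecutive records of the same term within a subject, fixed before unblinding.

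**Cost.** About a sentence in each document and one programming step. No added subjects, visits or assessments.
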